7.3. Lost to Follow-up

A participant will be considered lost to follow-up if he or she repeatedly fails (>2 times) to return for scheduled visits and is unable to be contacted by the study site.

The following actions must be taken if a participant fails to return to the clinic for a required study visit:

- The site must attempt to contact the participant and reschedule the missed visit as soon as possible and counsel the participant on the importance of maintaining the assigned visit schedule and ascertain whether or not the participant wishes to and/or should continue in the study.
- Before a participant is deemed lost to follow-up, the investigator or designee must make every effort to regain contact with the participant (where possible, 3 telephone calls and, if necessary, a certified letter to the participant's last known mailing address or local equivalent methods). These contact attempts should be documented in the participant's medical record.
- Should the participant continue to be unreachable, he/she will be considered to have withdrawn from the study and lost to follow-up.
- The participant is not considered lost to follow up until the last scheduled visit for that individual participant.

Discontinuation of specific sites or of the study as a whole are handled as part of Study and Site Start and Closure, [Section 10.1.9](#).

8. STUDY ASSESSMENTS AND PROCEDURES

- Study procedures and their timing are summarized in the SoA ([Section 1.3](#)).
- Immediate safety concerns should be discussed with the sponsor's Medical Monitor immediately upon occurrence or awareness to determine if the participant should continue or discontinue study intervention.
- Adherence to the study design requirements, including those specified in the SoA is essential and required for study conduct. Changes in study visit schedules or missed visits that lead to missing study information, must capture the specific information that explains the basis of missing data.
- All screening evaluations must be completed and reviewed to confirm that potential participants meet all eligibility criteria. Screen failure reasons will be captured in the interactive response technology (IRT) system.
- After screening procedures have been completed and eligibility criteria have been confirmed, eligible participants will be provided with instructions on how to discontinue any excluded medications. Document that the investigator has determined that discontinuation is safe and medically appropriate, the Medical Monitor has approved, and the discontinuation is medically supervised.
- Diaries and Questionnaires will be in electronic format within a secure application uploaded to the subject's mobile phone or tablet computer device of choice for personal completion. Site personnel will be able to provide instruction for uploading, use, and completion of the electronic diaries (e-diaries) and electronic questionnaires (e-questionnaire). The application is secure with unique username and password for access.
- Lab analyte measures and ECGs will be read by qualified personnel at the site (eg, a physician)
- Repeat or unscheduled samples may be taken for safety reasons or for technical issues with the samples.

8.1. General Administrative Procedures

8.1.1. Informed Consent

The investigator or medically qualified designee (consistent with local requirements) must obtain documented consent from each potential participant/legal representative prior to participation in this study. A signed copy of the ICF should be given to the participant and the original should be placed in the participant's medical records.

8.1.2. Assignment of Participant Number

Each participant who signs the ICF will be assigned a unique number that will identify the participant throughout the study. Once a number has been assigned, it cannot be reassigned to another study participant.

8.1.3. Medical History

Medical history of study participants will be obtained by the investigator or a medically qualified designee (consistent with local regulations). All active conditions, and any condition diagnosed within the participant's lifetime that the investigator deems clinically significant, will be recorded.

8.1.4. Medication Review (Prior and Concomitant Medications)

The investigator or medically qualified designee should review the participant's prior medication use, including over-the-counter medications, health, and dietary supplements. Any medication that is required to be washed out prior to the study should also be recorded. All medications currently taken by the participant should be recorded and reconciled for compliance with the protocol.

8.1.5. Inclusion and Exclusion Criteria Review

All inclusion and exclusion criteria should be reviewed by the investigator to ensure the participant qualifies for the study.

8.1.6. Timing of Study Intervention Dosing

Participants will be instructed to dose XYWAV according to the following guidelines-

- On the first night of administering the study intervention drug (XYWAV), initiate treatment at the same dose and regimen as Xyrem, while maintaining the dose and regimen of any concomitant anticonvulsants or stimulants unchanged throughout the study.
- Initially, as with Xyrem, wait at least 2 hours after the last meal before taking XYWAV.
- Once the investigator determines that a stable dose and regimen has been achieved, XYWAV can be taken with or without food. If needed, XYWAV will be titrated to an optimized dose and regimen based on efficacy and tolerability, under the advisement and instruction of the investigator.

8.2. Effectiveness Assessments

Planned time points for all effectiveness assessments are provided in the SoA (Section 1.3).

8.2.1. Rate of Cataplexy Incidents

The change in weekly rate of cataplexy attacks (for NT1) will be assessed. Participants will complete an electronic Cataplexy Frequency Diary ([Appendix 5](#)) each night prior to bedtime, to record the number of daily cataplexy attacks experienced, in accordance with the SoA (from the Baseline period through to the ET or E/D, as applicable). The study staff will review the diary at each study visit and discuss it with the subject at the phone/visit contact, see [Section 9.4.2](#).

8.2.2. Epworth Sleepiness Scale

The ESS questionnaire ([Johns 1991](#), [Johns 2000](#), [Broderick 2013](#)) includes a set of 8 questions regarding how likely the participant would be to doze off or fall asleep in different situations. Responses range from 0 = would never doze, to 3 = high chance of dozing. As such, the ESS provides a measure of EDS or average sleep propensity in daily life.

A self-administered, electronic ESS questionnaire will be completed by the participants at the baseline visit and the ET or E/D visits, as indicated in the SoA (Section 1.3), with appropriate training, instructions and supervision provided for completing the questionnaires, as needed.

8.2.3. Participant Global Impression of Change (PGIC)

The PGIC is a 7-point Likert-type rating based on a 7-point scale ranging from 1 (very much improved) to 7 (very much worse) that is widely used to assess efficacy in clinical drug trials ([Schmitt 2014](#); [Bogart 2017](#)). The PGIC assessment will be administered in electronic format to participants at the ET or E/D visits, as indicated in the SoA (Section 1.3), with appropriate training, instructions and supervision provided for completing the assessment, as needed.

8.2.4. Dose and Regimen Changes in Intervention Period

To evaluate treatment optimization with XYWAV during the Intervention period, the number of changes from the first dose and regimen to an optimized dose and regimen and the time taken to achieve the optimized dose and regimen will be measured, as described in [Section 9.4.2](#).

Additionally, the number of participants dosing fasted versus dosing without consideration of food, and the timing and characterization of meals with regard to dosing will be summarized descriptively. These assessments will utilize participant data collected using a self-administered, electronic Food and Drug Dosing Diary ([Appendix 4](#)) completed by participants daily (Section 9.4.2).

8.2.5. Ease of Switching Medication Scale (EOSMS)

To assess the ease of switching treatment from Xyrem to XYWAV, the EOSMS Questionnaire ([Appendix 8](#)) will be administered in electronic format to participants at the ET or E/D visits, as indicated in the SoA (Section 1.3).

8.2.6. Forced Preference Questionnaire (FPQ)

To evaluate participant preference for study medication, the FPQ Questionnaire ([Appendix 9](#)) will be administered in electronic format to participants at the ET or E/D visits, as indicated in the SoA ([Section 1.3](#)).

8.3. Safety and Tolerability Assessments

Planned time points for all safety and tolerability assessments are provided in the SoA (Section 1.3).

8.3.1. Physical Examinations

- A complete PE will include, at a minimum, assessments of the cardiovascular, respiratory, gastrointestinal and neurological systems; breast and genitourinary exams are excluded.
- Investigators should pay special attention to clinical signs related to previous serious illnesses.
 - Any abnormalities identified at the screening PE should be recorded as medical history.

8.3.2. Vital Signs

- Vital signs to be measured (before blood collection, when applicable) will include oral temperature, heart rate (HR), respiratory rate (RR), and BP at the times specified in the SoA (Section 1.3).
- Blood pressure and pulse measurements will be assessed with a completely automated device.
- Blood pressure and pulse measurements should be preceded by at least 5 minutes of rest for the participant in a quiet setting without distractions (eg, television, cell phones).
- Vital signs will be measured in a semi-supine position after 5 minutes of rest period

8.3.3. Electrocardiograms

Single 12-lead ECG will be obtained for screening purposes only, as outlined in the SoA (see Section 1.3) using an ECG machine that automatically calculates the HR and measures PR, QRS, and QT intervals.

8.3.4. Clinical Safety Laboratory Assessments

Clinical laboratory assessments to be conducted in the study are listed in [Table 5](#).

Table 5. List of Clinical Laboratory Tests

Hematology:	Serum Chemistry:
- Complete blood count (CBC), including platelet count and white blood cell count (WBC) with differential	- Albumin (ALB) - Alkaline phosphatase (ALK-P) - Alanine aminotransferase (ALT; SGPT) - Aspartate aminotransferase (AST; SGOT) - Blood urea nitrogen (BUN) - Calcium (Ca) - Chloride (Cl) - Creatinine - Creatine kinase - Gamma-glutamyl transferase (GGT) - Globulin - Glucose - Lactate dehydrogenase (LDH) - Phosphorus - Potassium (K) - Sodium (Na) - Magnesium - Total bilirubin - Direct bilirubin - Total cholesterol - Total protein - Triglycerides - Uric acid - Thyroid stimulating hormone (TSH)(screening only)
Urinalysis:	
- Appearance - Bilirubin - Color - Glucose - Ketones - Nitrite - Occult blood - pH - Protein - Specific gravity - Urobilinogen	
*Serum Pregnancy Screen	
Drug Screen (urine)	
Alcohol Screen	

*Pregnancy screening is required for all females of childbearing potential. Female subjects who have undergone surgical sterilization, who are post-menopausal (defined as >1 year of amenorrhea), who have medically documented ovarian failure (defined as serum estradiol and follicle-stimulating hormone [FSH] levels within the institutional postmenopausal range and a negative serum or urine β HCG) do not need to undergo pregnancy screening.

- Clinical laboratory tests will be performed at the study time points indicated in the SoA (Section 1.3). Accordingly, certain clinical laboratory assessments (eg, comprehensive metabolic panel, hematology, urinalysis, TSH and serum pregnancy testing) will be performed for screening purposes only, whereas other clinical laboratory assessments (eg, urine drug and alcohol screening) will be performed at various study time points, as indicated per the SoA (see Section 1.3).
- All protocol-required laboratory tests (Table 5 and SoA) must be conducted in accordance with the laboratory manual.

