5. STUDY POPULATION

The intended study population includes participants currently taking Xyrem for narcolepsy. Specifically, participants must have been maintained on a stable Xyrem dose and regimen, at any prescribed dose administered once, twice, or thrice nightly for no less than 2 months, up to a maximum nightly dose of 9 grams, with no single dose exceeding 6 grams.

Prospective approval of protocol deviations to recruitment and enrollment criteria, also known as protocol waivers or exemptions, is not permitted.

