5.1. Inclusion Criteria

Participants are eligible to be included in the study only if all of the following criteria apply:

Age

1. Participant must be 18 to 80 years of age (inclusive), at the time of signing the informed consent.

Type of Participant and Disease Characteristics

2. Participants who have a primary diagnosis of Type 1 or Type 2 narcolepsy that meets ICSID-3 criteria or DSM-5 criteria ([Ruoff and Rye 2016](#)), and are being currently treated with Xyrem, with or without additional anticataplectics or stimulants.
3. Participants who have been taking Xyrem (with or without additional anticataplectics or stimulants eg, TCA, SNRI, SSRI, atomoxetine) in a stable dose and regimen for at least two months prior to screening, with evidence of clinical improvement on their current regimen, per the investigator's judgement. Only Xyrem will be substituted with XYWAV, with dose and regimen of any concomitant anticataplectics or stimulants remaining unchanged throughout the study.

Sex and Contraceptive/Barrier Requirements

4. Participant is male or female
 - A female participant is eligible to participate if she is not pregnant or breastfeeding, and one of the following conditions applies:
 - Is a woman of non-childbearing potential (WONCBP) as defined in [Appendix 3](#)
OR
 - Is a WOCBP and using a contraceptive method that is highly effective (with a failure rate of < 1% per year), preferably with low user dependency, as described in [Appendix 3](#), during the study Intervention period and for at least 7 days after the last dose of study intervention. The investigator should evaluate the potential for contraceptive method failure (eg, noncompliance, recently initiated) in relationship to the first dose of study intervention.
 - A WOCBP must have a negative highly sensitive pregnancy test (serum) during screening (see [Section 8.3.5](#)).
 - The investigator is responsible for review of medical history, menstrual history, and recent sexual activity to decrease the risk for inclusion of a woman with an early undetected pregnancy.

Informed Consent

5. Capable of giving signed informed consent as described in [Section 10.1.3](#), which includes compliance with the requirements and restrictions listed in the informed consent form (ICF) and in this protocol.

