8.3.5. Pregnancy Testing

- Refer to [Section 5.1](#) for pregnancy testing entry criteria.
- Pregnancy testing (serum) should be conducted as specified in the SoA ([Section 1.3](#)).
- Additional serum pregnancy tests may be performed, as determined necessary by the investigator or required by local regulation, to establish the absence of pregnancy at any time during the participant's participation in the study.

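### Table 5 footnote: the undefined surgical-sterilization exemption, read in its ordinary sense, skips the screening pregnancy test for women with bilateral tubal occlusion, whom inclusion criterion 4 requires to be tested

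*Protocol*

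**What the plan says.** **Laboratory table.** The footnote to protocol Table 5 (Section 8.3.4) has two parts. The first is a general rule: "Pregnancy screening is required for all females of childbearing potential". The second exempts three groups, starting "Female subjects who have undergone surgical sterilization, who are post-menopausal (defined as >1 year of amenorrhea" and ending with medically documented ovarian failure. No sterilization procedure is named, and Appendix 3 is not mentioned.

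**Eligibility.** Section 5.1 opens with "Participants are eligible to be included in the study only if all of the following criteria apply". Under criterion 4 a woman enters either as a woman of non-childbearing potential as defined in Appendix 3, or as a WOCBP using a highly effective method described there. The criterion adds: "A WOCBP must have a negative highly sensitive pregnancy test (serum) during screening".

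**Appendix 3.** A woman counts as fertile from menarche until menopause unless she is permanently sterile. The permanent methods named for this study are hysterectomy, bilateral salpingectomy and bilateral oophorectomy. Bilateral tubal occlusion appears in the separate table of allowed contraceptives, under highly effective methods with low user dependency.

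**Timing.** The Schedule of Activities (Section 1.3) and Section 8.4.5 place the serum test at screening only.

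**SAP.** The Table 3 footnote (Section 10.4) repeats the protocol footnote. Section 10.5 makes the testing requirement subject to the exemptions in Table 3.

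**The concern.** A site that uses the laboratory table to decide whom to test finds an exemption that looks complete in itself, with its own definitions. A coordinator could reasonably regard a woman with tubal occlusion as surgically sterilized and omit the test. She would then be enrolled without meeting criterion 4, in a protocol whose Section 5 states: "Prospective approval of protocol deviations to recruitment and enrollment criteria, also known as protocol waivers or exemptions, is not permitted". The only scheduled laboratory check behind the pregnancy exclusion (exclusion criterion 16) would also be missing for her. The stakes are an avoidable eligibility deviation and the loss of one safety check.

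**Working it through.** The main check is a comparison of rules. There is no plan figure to reproduce.

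**Step 1. Classify the woman.** Take a pre-menopausal woman with bilateral tubal occlusion.

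| Source | Status | Scheduled serum tests |
|---|---|---|
| Criterion 4 with Appendix 3 | Method is on the contraceptive list and not on the permanent-sterilization list, so WOCBP | 1 |
| Table 5 footnote, exemption sentence, ordinary meaning | Surgically sterilized, so exempt | 0 |
| Table 5 footnote, first sentence, with Appendix 3 definitions | WOCBP, so tested | 1 |

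**Step 2. Check the inference about Appendix 3.** The appendix says its permanent methods include the three procedures, so the list may not be exhaustive. The structure still points one way for tubal occlusion. Criterion 4 offers two routes, non-childbearing status or a listed contraceptive. Tubal occlusion sits on the second list and is absent from the first, and none of the three permanent procedures appears among the contraceptives.

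**Step 3. Check which reading of the footnote is live.** SAP Section 10.5 treats the footnote's second sentence as a set of exceptions to the childbearing-potential rule. That supports the reading in the second row of the table, although it does not prove that sites read it so.

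**Step 4. Decide which rule governs.** Section 8.3.5 says "Refer to [Section 5.1](#) for pregnancy testing entry criteria", and Section 8.1.5 says "All inclusion and exclusion criteria should be reviewed by the investigator to ensure the participant qualifies for the study". Together with the all-criteria rule in Section 5.1 and the bar on waivers in Section 5, this makes criterion 4 the controlling text and the footnote the text to change.

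**Step 5. Rough size of the safety effect.**
- Input: a failure rate below 1% per year with consistent and correct use (Appendix 3, contraceptive table, note b).
- Assumptions: a constant rate and, as an extreme, all 100 planned participants being women who rely on tubal occlusion.
- Expected pregnancies conceived in any six-week span, the length of the Intervention period: 100 × 0.01 × 6/52 = 0.115, so fewer than about 0.12.
- The figure scales with the subgroup. With 10 such women it would be below 10 × 0.01 × 6/52 = 0.012.

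The documents do not give the true number of women. Note b also says that typical-use rates differ, so this is an order of magnitude and not a strict bound.

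**The case against.** The strongest reply is that there is no real conflict. The footnote never mentions tubal occlusion, and its first sentence already requires testing in every woman of childbearing potential. The second sentence can be read as describing who falls outside that group, with the study's own definitions applying. Section 8.3.5 follows directly and sends the site to Section 5.1, where criterion 4 cites Appendix 3. A site must settle childbearing status under Appendix 3 before it can enroll any woman.

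Much of this stands. The conflict depends on the ordinary meaning of an undefined term and on a classification inferred from two lists, and a careful site would reach the right answer. But a route to the governing text does not make the footnote correct. Its exemption sentence supplies definitions that differ from Appendix 3 and gives no sign that a narrower list exists.

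The reply on consequences also stands. Tubal occlusion is rated highly effective, and criterion 4 separately requires "review of medical history, menstrual history, and recent sexual activity to decrease the risk for inclusion of a woman with an early undetected pregnancy". Section 8.3.5 allows additional tests at the investigator's discretion, and participants are already taking oxybate as Xyrem.

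A reader might go further and infer that the protocol waives an eligibility test, or that pregnant women would be enrolled in meaningful numbers. The documents support neither. Criterion 4 is not waived, and the subgroup is unknown and at low risk. A reader might also see a second conflict in the unqualified year of amenorrhea, because Appendix 3 excludes amenorrhea with another medical cause. That mismatch is arguable, and nothing here rests on it.

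**Conclusion.** The point holds as a minor inconsistency. On the ordinary reading of surgical sterilization, the Table 5 footnote omits a test that criterion 4 requires for a woman with bilateral tubal occlusion: 0 scheduled tests instead of 1. It rests on two assumptions: that sites would take the term to include tubal occlusion, and that Appendix 3's placement of the procedure makes her a WOCBP. Both are reasonable, and neither is stated outright.

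The consequence is a possible eligibility deviation and one missed safety check per affected woman. No endpoint or analysis changes. The number of affected women is unknown, and counting procedures on which the rules differ would not measure it.

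**What to change.** **Protocol.** Keep the first sentence of the Table 5 footnote and replace the exemption list with: *Women who are not of childbearing potential per Appendix 3 do not need to undergo pregnancy screening.* This also moves the menopause and ovarian-failure exemptions onto Appendix 3's rules, so one set of definitions applies throughout.

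**SAP.** Align the Table 3 footnote and Section 10.5. This is for consistency only, since the SAP does not decide who is tested.

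**If screening is closed.** The protocol edit then has no effect, and a retrospective check is needed. SAP Section 10.5 plans only a listing of pregnancy results. Nothing says that it shows sterilization method or women with no result, so it cannot do the job alone. Cross-check coded surgical history (SAP Section 8.4) and the childbearing-potential field (SAP Section 8.3) against the pregnancy results. Surgical history matters most, because a site that misapplied the footnote may have recorded the woman as not of childbearing potential. Record each enrolled woman with tubal occlusion and no test as an eligibility deviation.

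**Cost.** One footnote in the next amendment, with IRB/IEC approval, and two SAP wording edits. Any extra serum tests could use the screening visit at which chemistry, hematology and TSH are already collected, so no visit is added. Enrollment status is not stated. The SAP cites a protocol dated 08Dec2020 with a planned duration of about 17 months, and SAP V1.1 is dated 12 DEC 2022, so screening may already be over.
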